### **4.2 Handling of Dropouts**

A participant who discontinues study participation prematurely for any reason is defined as a dropout if the participant has already been administered at least one dose of study drug.

The reasons for withdrawal will be listed in a table. Dropouts will be included in all safety analyses. They will also be included in efficacy analyses if the treatment duration is  $\geq 3$  months. The ABR will be calculated for these participants. It is assumed that a shorter treatment duration will not be sufficient to correctly estimate the ABR and would bias the results. When calculating ABRs, the end of the measuring period for a dropout is defined as the later of last available infusion record from the electronic patient diary (ePD) or the last procedure in a scheduled visit, excluding the final visit.

### **4.3 Handling of Missing Data**

All missing or partial data will be presented in the subject data listings as they are recorded on the Case Report Form (CRF).

#### **General rules**

When appropriate, the following imputation rules will be implemented so as not to exclude participants from statistical analyses due to missing or incomplete data:

- **Missing time of infusions**

If an in-hospital infusion has a missing time, the time of the pre-infusion FVIII level measurement plus 1 minute will be used. If this time is also missing, 10:00 will be substituted.

- **Missing or incomplete adverse event (AE) start date**

If first study treatment falls within imputation range, incomplete start date is imputed as first day of treatment. Otherwise, it is imputed to the earliest date of the imputation interval.

Empty start date is not imputed. Incomplete stop date is always imputed as the latest date of the imputation interval. Empty stop date is not imputed and presumed to be ongoing.

- Missing or incomplete concomitant medication start and end date**

If first study treatment falls within imputation range, incomplete start date is imputed as first day of treatment. Otherwise, it is imputed to the earliest date of the imputation interval.

Empty start date is not imputed. Incomplete stop date is always imputed as the latest date of the imputation interval. Empty stop date is not imputed and presumed to be ongoing.

Partially missing dates of medications categorized as 'PRIOR FVIII THERAPY' will not be imputed. All these medications will be considered prior medications.

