### 8.3.1 Time Period and Frequency for Collecting AE and SAE Information

All AEs and SAEs will be collected from the signing of the informed consent form (ICF) until the end of the final study visit at the time points specified in the SoA (Section [1.3](#)).

Medical occurrences that begin before obtaining informed consent but are diagnosed at screening or during the screening period (e.g., abnormal lab values) will be recorded on the Medical History/Current Medical Conditions section of the case report form (CRF), not the AE section.

All SAEs will be recorded and reported to the sponsor or designee immediately and under no circumstances should this exceed 24 hours, as indicated in Section [10.3](#). The investigator will submit any updated SAE data to the sponsor within 24 hours of it being available.

Investigators are not obligated to actively seek AE or SAE after conclusion of the study participation. However, if the investigator learns of any SAE, including a death, at any time after a participant has been discharged from the study, and he considers the event to be reasonably related to the study intervention or study participation, the investigator must promptly notify the sponsor.

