### **6.4 Safety**

All safety analyses will be performed on the SAF. MedDRA codes of studies 13024 and 15912 will be updated by the MedDRA version used for study 19764. An AE will be considered treatment-emergent if it starts after first injection and not later than 7 days after last injection of Jivi.

Overview tables displaying all AEs, all pre-treatment AEs and all treatment emergent adverse events (TEAEs) will be created. All subsequent tables will be presented by MedDRA preferred term (PT) and system organ class (SOC). Serious AEs, TEAEs, serious TEAEs, drug-related TEAEs, serious drug-related TEAEs, TEAEs of special interest, TEAEs causing discontinuation of study drug, TEAEs by maximum intensity, drug-related TEAEs by maximum intensity, non-serious TEAEs, and AEs leading to death will be presented.

Overview tables, all TEAEs, serious TEAEs, drug-related TEAEs and serious drug-related TEAEs will be displayed by subgroups.

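### An incomplete AE start date is moved to the first treatment day without checking the stop date, so an event that ended in screening can be counted as a TEAE

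*SAP*

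**What the plan says.** SAP 4.3 (General rules) gives adverse events and concomitant medications the same date rules:

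- Partial start date whose range contains the first treatment: "If first study treatment falls within imputation range, incomplete start date is imputed as first day of treatment".
- Partial start date in any other case: "Otherwise, it is imputed to the earliest date of the imputation interval".
- Fully missing start date: "Empty start date is not imputed".
- Partial stop date: "Incomplete stop date is always imputed as the latest date of the imputation interval". A missing stop date is taken as ongoing.

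The stop-date rule stands alone; nothing in it limits the start date. One group is exempt: medications categorised as prior FVIII therapy keep their partial dates and are always classed as prior.

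SAP 6.4 then classifies on the start date only: "An AE will be considered treatment-emergent if it starts after first injection and not later than 7 days after last injection of Jivi". Protocol 9.4.2 has the same definition. Protocol 8.3.1 sets the collection window: "All AEs and SAEs will be collected from the signing of the informed consent form (ICF) until the end of the final study visit". The Schedule of Activities puts screening 2 to 8 weeks before baseline, so events that begin and end before the first injection will be on the database. SAP 6.4 plans overview tables for all, pre-treatment and treatment-emergent events. SAP 6.1 tabulates certain new concomitant medications that started after first treatment.

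**The concern.** Moving an uncertain onset to the first treatment day is a common, cautious device: if the event might have begun on treatment, count it as such. That reasoning fails when the stop date shows that the event was over before the first injection. Applied without that check, the rule produces a start later than the stop and moves a resolved screening event into the treatment period.

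TEAE incidence is a secondary safety endpoint of a study whose stated purpose is safety. A date rule should not create on-treatment events from pre-treatment ones, particularly when the contradicting stop date is already in the record. The same applies to the table of new concomitant medications.

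**Working it through.** The plan gives no figure to reproduce, so the check applies the written rules to test dates and then asks how often they would bite.

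**Step 1. Test dates.** First injection on 20 March 2020. The inclusive reading counts a start on the first treatment day as after first injection; the strict reading does not.

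| Recorded start | Stop | Imputed start | Inclusive | Strict |
|---|---|---|---|---|
| March 2020 | 5 March | 20 March (15 days after stop) | TEAE | not TEAE |
| 2020 | 25 February | 20 March (24 days after stop) | TEAE | not TEAE |
| February 2020 | 25 February | 1 February | not TEAE | not TEAE |
| March 2020 | 2 April | 20 March | TEAE | not TEAE |

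The first two rows show the fault. The third shows its limit: if the range does not contain the first injection, the event stays pre-treatment. The fourth shows which reading must be intended. On the strict reading, even an event still present after treatment began fails the definition once it is imputed to the first treatment day, so the imputation would achieve nothing. The inclusive reading is the only one on which the rule works, and on that reading the first two rows are misclassified.

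**Step 2. How often, given a partial start date.** The documents give no count of partial dates, so this is conditional and rests on assumptions: onset uniform over the screening window, duration 1 to 7 days, stop date known and before the first injection, first injection on each day of 2020 in turn, inclusive reading. Share of such events relabelled as TEAEs:

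| Screening length | Start day missing | Start day and month missing |
|---|---|---|
| 14 days | 66 to 75% | 97 to 98% |
| 28 days | 43 to 53% | 95 to 96% |
| 56 days | 19 to 26% | 91 to 92% |

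Shorter screening makes it likelier that onset and first injection share a calendar month. These are shares of events that already have a partial start date, not of all adverse events.

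**Step 3. After the fix.** If the first-treatment-day rule applies only when the stop date is missing or not before the first injection, every event in Step 2 stays pre-treatment: 0% relabelled.

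**Step 4. Weight of one participant.** With 25 to 30 treated (protocol synopsis), 1/30 = 3.3% and 1/25 = 4.0% of a study row. In the pool, protocol 9.2 expects 134 + 73 + at least 25 = at least 232, so 1/232 = 0.43% at most.

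**The case against.** Five arguments can be made for the plan.

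- **The range could be read as bounded by the stop date.** SAP 4.3 does not define the imputation range. If it means the dates on which the event could have started, a stop on 5 March closes it before 20 March, the start becomes 1 March, and the event stays pre-treatment. That would be the right result, but it is not written.
- **The rules are qualified.** They apply "When appropriate, the following imputation rules will be implemented so as not to exclude participants from statistical analyses due to missing or incomplete data". A programmer could decline to apply them to an impossible date. No criterion is given, so this does not settle what will be done.
- **On a strict reading of the definition, the example is not a TEAE.** True, but Step 1 shows that this reading also defeats the imputation.
- **Affected records remain visible.** Partial dates are listed as recorded, and all adverse events and pre-treatment events have their own overviews. This allows detection; it does not correct the TEAE tables.
- **Pooled consistency.** SAP 4.1 requires data handling consistent with studies 13024 and 15912, whose SAPs are not available here. This stands as a condition on the fix, not as a reason to keep a start date after a stop date.

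Two stronger readings are tempting. A reader might infer that an event with an empty start date can never be treatment-emergent. The SAP says only that the date is not imputed and gives no classification; that is a missing rule, not an exclusion. A reader might also infer that a reaction at the first injection would be lost because the definition says after. That needs the strict reading, which is incompatible with the main point. The first injection is given in hospital with an adverse-event review, and hypersensitivity is a reportable event of special interest, so tabulating such a reaction as pre-treatment would take an unusually literal programming choice. What remains is that Day 1 handling is not defined.

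**Conclusion.** The point holds in one direction. As written, SAP 4.3 can give an adverse event a start date after its own stop date, and SAP 6.4 can then count an event that ended in screening as treatment-emergent. The same mechanism can make a medication stopped before treatment look new. The conclusion assumes that a start on the first treatment day counts as after first injection, and that the imputation range is not silently cut at the stop date.

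The documents do not support a claim of misclassification in both directions: for empty start dates and Day 1 onsets the plan is silent or ambiguous, not demonstrably wrong.

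The size is small and not fully known. Only partial start dates spanning the first injection are exposed to the main fault, and their number is not given. All analyses are descriptive, and FVIII inhibitor development does not depend on these dates. The correction is worth making because a written rule gives a wrong result and one sentence repairs it.

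**What to change.** **Main change, SAP 4.3, for adverse events and concomitant medications.** Impute the first treatment day only if the recorded or imputed stop date is missing or is not before the first injection. Otherwise impute the earliest date of the interval and classify the record as pre-treatment (for a medication, prior). Because a partial stop date is set to its latest possible date, uncertain cases still fall on the treatment-emergent side.

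**Secondary clarifications, SAP 6.4.**

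- A start on Day 1, whether imputed or recorded without a time, counts as treatment-emergent unless recorded as pre-injection.
- An adverse event with an empty start date counts as treatment-emergent unless its stop date is before the first injection.

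**Pooled tables.** Check the rules used for studies 13024 and 15912 and align them. Since protocol 9.4.2 carries the same TEAE definition, record the Day 1 statement as a clarification in the SAP's document history.

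**Cost.** A few sentences, a small macro change and the check against the two earlier studies. TEAE counts may shift slightly either way: the stop-date condition can only lower them, and the default for empty start dates may raise them.

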### Additional descriptive analyses in the presence of missing data

The number of participants who prematurely discontinue the study for any reason, as well as the time point and reasons for premature discontinuation of study, will be reported. The number of missing FVIII inhibitor and anti-drug or anti-PEG antibody measurements will be provided.

## 4.4 Interim Analyses and Data Monitoring

An optional interim analysis might be performed, if needed for regulatory submission or publication purposes, after all participants have been treated for 6 months for assessment of the main safety (inhibitor development) and efficacy endpoints.

The scope of the interim analysis will depend on its purpose and will be defined in an SAP supplement, if needed.

There will be no Data Safety Monitoring Board (DSMB) for this study.

## 4.5 Data Rules

The following derivation rules will be applied to this study:

### Counting of bleeds:

- 'All bleeds' will include all bleeds, regardless of treated or untreated (untreated bleeds will only be available from study 19764)
- A bleed will be counted as treated bleed if either the flag variable from the diary indicates that the bleed was treated or there is a matching infusion for this bleed (regardless of product used).

### ABR:

$$\text{Annualized number of bleeds} = \frac{\# \text{ of bleeds} * 365.25 * 24 * 60}{\text{period}}$$

*Period* is defined as the number of minutes calculated from the date and time of the beginning of the evaluation period and the date and time of the end of the evaluation period.

Evaluation periods for study 19764:

- Main efficacy period: Time from injection at visit 3 to end of treatment
- Complete study: Time from first injection at visit 2 to end of treatment

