### 8.1.1 Treatment Logs/Bleeding Verification

Treatment logs are commonly used for hemophilia participants for documentation of their home treatment. Home treatment and bleeding information are the key variables for evaluation of efficacy. Study specific treatment logs will be provided in national language. The system for this study will be electronic patient diary (EPD) devices since they are interactive, allow for real time data transmission, record-stamp date and time of fulfillment and facilitate the clarification of data with the site and also the data cleaning process.

Participants will be provided with EPDs for the whole study. At Screening visit, participants will be trained in the use of the device. These logs will be used to collect the treatment data and bleeding episodes by the participants, and the data will be verified for accuracy and completion by the investigator or delegate during regularly scheduled interactions with the participant. Thus, the EPD will be considered the source for these data.

For each self-administered injection of Jivi, information must be recorded on the EPD as follows:

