#### Each injection of Jivi:

- a. Date and time
- b. Injection record
- c. Individual vial number (bar code scan from vial label or manual entry) and units administered
- d. Reason for treatment

Prophylaxis

Spontaneous bleed first treatment

Trauma bleed first treatment

Follow-up treatment

Other

Injections of Jivi as part of protocol mandated visits and procedures will be recorded on the respective CRF pages.

All bleeding episodes (regardless if treated or not, or treated at home or under medical supervision) as well as any potential treatment with other hemophilia drugs will be recorded in the EPD:

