## Statistical Analysis Plan

BAY 94-9027 / 19764

Page: 9 of 17

End of treatment is defined as date of latest infusion plus 7 days or end of study, whatever is earlier.

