#### Modified Intent-to-treat set (mITT)

A participant will be included in the mITT if he received at least 1 infusion of study drug and has injection/bleeding data for at least 3 months available.

A participant of study 13024 or study 15912 will only be included in the mITT if he entered the extension phase of the study.

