### Sensitivity analyses:

- Estimates and 95% confidence intervals from a negative binomial regression model will be presented for the ABRs of all bleeds, different lengths of evaluation periods will be addressed via an offset variable
- A subject listing including number and kind of bleeds and time in study will be provided for participants excluded from the mITT set

CCI

CCI

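### The ABR period is unbroken elapsed time, so a diary lapse inside it counts as bleed-free and no planned ABR analysis corrects for this

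*SAP*

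**What the plan says.** **Denominator.** In SAP 4.5 the ABR period "is defined as the number of minutes calculated from the date and time of the beginning of the evaluation period" to the date and time of its end. There are two periods: "Main efficacy period: Time from injection at visit 3 to end of treatment" and "Complete study: Time from first injection at visit 2 to end of treatment". The end is fixed by this rule: "End of treatment is defined as date of latest infusion plus 7 days or end of study, whatever is earlier". For dropouts, SAP 4.2 sets a different end: the later of the last diary infusion record and the last procedure at a scheduled visit, with the final visit left out.

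**Numerator.** Protocol 8.1.1 sends every bleed to the diary, treated or not and wherever treated, and says of home treatment and bleeding data: "Thus, the EPD will be considered the source for these data". Under Protocol 8.3.6 a bleed is not reported as an adverse event unless it is serious. Injections at study visits take another route: "Injections of Jivi as part of protocol mandated visits and procedures will be recorded on the respective CRF pages".

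**Missing data.** Protocol 9.4 promises that the SAP will deal with missing data. SAP 4.3 covers infusion times, adverse event dates and medication dates, and counts missing inhibitor and antibody results. It does not mention diary time. The mITT requires that a participant "has injection/bleeding data for at least 3 months available" (SAP 5.1) and does not tie that amount to the length of the period.

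**Sensitivity analysis.** In the negative binomial model, "different lengths of evaluation periods will be addressed via an offset variable" (SAP 6.2).

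**The concern.** The numerator depends on diary entry and the denominator does not. If a participant stops recording for a while and then resumes, the silent stretch stays in the denominator, and any bleeds in it never reach the numerator. If no bleed occurred, there is no error. If one did, the ABR is too low. The error cannot run the other way.

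The same holds for silence just before the Last Visit in a participant who completes. The in-hospital injection there is recorded on the CRF and counts as the latest infusion, so it closes the period even when the diary lapsed earlier.

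SAP 6.2 names ABR as the main efficacy endpoint of the secondary objective, and the study expects about 25 to 30 participants, so a few poor diarists can move the summary. The negative binomial model cannot reveal the problem because its offset is the same elapsed time.

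**Working it through.** The documents state no ABR value and no diary-gap rate, so there is no figure to reproduce. Gap lengths and the bleed rate below are assumptions.

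**1. Formula.** ABR = bleeds × 365.25 × 24 × 60 / period in minutes. Unit check: 4 bleeds in 365.25 days gives 4.00.

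**2. Length of the main efficacy period.** Visit 3 falls at 10–15 exposure days (ED) and the study runs to 100 ED, so 85 to 90 dosing intervals remain:
- 2x/week: 85 × 3.5 to 90 × 3.5 = 297.5 to 315 days (use 300)
- every 5 days: 85 × 5 to 90 × 5 = 425 to 450 days (use 440)
- every 7 days: 85 × 7 to 90 × 7 = 595 to 630 days (use 620)

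**3. Effect of a gap.** With an undocumented gap of g days inside an elapsed period of T days and a constant bleed rate, reported ABR / ABR over documented time = (T − g)/T = 1 − g/T. With an assumed rate of 4 bleeds per year:

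| T (days) | g = 14 | g = 30 | g = 60 | g = 90 |
|---|---|---|---|---|
| 300 | 3.81 | 3.60 | 3.20 | 2.80 |
| 440 | 3.87 | 3.73 | 3.45 | 3.18 |
| 620 | 3.91 | 3.81 | 3.61 | 3.42 |

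The relative shortfall runs from 14/620 = 2% to 90/300 = 30%. If the gap instead lengthens the time needed to reach 100 documented ED, the ratio is T/(T + g), and the extremes become 620/634 = 0.978 and 300/390 = 0.769, or 2% to 23% low.

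**4. Cohort mean.** If a share q of participants has such a gap and T = 440, the ratio is 1 − q × g/440. For q = 0.1 and g = 30 it is 0.993. For q = 0.4 and g = 90 it is 0.918. The mean is 0.7% to 8.2% low.

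**5. Silence after the last infusion.** Take 120 documented days followed by 60 silent days with no later infusion. The 7-day rule gives 120/127 = 0.945, where uncut time would give 120/180 = 0.667. Terminal silence is therefore mostly handled already.

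**The case against.** **Prevention.** Sites contact participants monthly to check the diary and check diary entries and bleeding history at each visit (Protocol 10.4). Investigators or delegates verify the data (8.1.1), vials are reconciled against the diary (6.4), and serious failure of entry leads to withdrawal (7.2). These controls make long gaps less likely, and that stands. But the withdrawal rule has no threshold, so lesser gaps stay in, and none of the controls alters the denominator.

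**Detection.** SAP 4.5 and 6.1 tabulate compliance, with a class below 95%, and the time between prophylaxis injections. These would flag many gaps. They cannot tell a skipped infusion from an unrecorded one, and they do not adjust the ABR.

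**Event-driven diary.** Entries are made for injections and bleeds, so silence between scheduled infusions is normal. Longer silence can also be skipped infusions with no bleeds, which is real bleed-free time. That stands, so the point covers only lapses clearly longer than the prescribed interval.

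**A stronger reading.** A reader might infer that a participant whose diary stops at Month 6 and who attends a Last Visit at Month 18 is reported at (183 − 63)/(548 − 63) = 25% of the true rate. A reader might also infer that the 3-month mITT minimum admits participants at 12.5% to 25% of it (91.3/730 to 91.3/365). The documents do not support either. The first participant has about 13 + 120/7 = 30 documented ED, and the second at most 91/3.5 = 26. Both fall far short of 100 ED and are dropouts on the documented data, so SAP 4.2 excludes the final visit from setting the end. Some dilution can remain when a later scheduled visit was attended: with Visit 5 at day 365, the first ratio is 120/302 = 0.40. That would need many monthly contacts to have failed.

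**Pooling.** SAP 4.1 requires data handling consistent with studies 13024 Part A and 15912, and ABRs are pooled. Replacing the main denominator in 19764 alone would break this. The objection stands and shapes the fix.

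**Conclusion.** The gap in the plan is real but limited. A diary lapse inside the evaluation period is counted as bleed-free, the effect can only lower the ABR or leave it unchanged, and the one model-based ABR sensitivity analysis shares it. Silence after the last infusion is already cut at 7 days, and the final visit cannot set the end for dropouts.

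The size is unknown because the documents give no gap rate. The working range is about 2% to 30% low for an affected participant (gaps of 14 to 90 days) and about 1% to 8% low for the cohort mean (10% to 40% of participants with gaps of 30 to 90 days). Both rest on a constant bleed rate that continues through the gap. All analyses are descriptive, so no hypothesis test is affected. The change is worth making but is not critical.

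**What to change.** Keep the elapsed-time ABR as the main and pooled analysis. In SAP 4.5 and 6.2 add, for study 19764, a pre-specified documented-time ABR:

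- **Undocumented time.** Define it from infusion records only, for example an interval between consecutive documented infusions that exceeds a pre-set length or a pre-set multiple of the prescribed interval. Exempt it if the monthly contact or visit source confirms bleeding status for that interval. A rule that also looks for bleed records would make the denominator depend on the outcome. Infusions given for bleeds carry some of the same dependence, so state whether they count or only prophylaxis infusions do.
- **Removal.** Take out both the time and any bleeds in those intervals.
- **End of period.** When the diary lapsed before the Last Visit, end documented time at the last diary infusion plus 7 days, not at the CRF-only Last Visit injection.
- **Consistency.** Use documented time as the negative binomial offset and for the 3-month minimum in this analysis.
- **Reporting.** List undocumented days per participant.

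In the same edit, reconcile the different period ends for dropouts in SAP 4.2 and 4.5.

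The cost is SAP wording and a short derivation from dates already collected. A little person-time is lost, including some that was truly bleed-free when infusions were skipped. The retained elapsed-time ABR covers that case, and close agreement between the two would show that diary gaps had little effect.
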